7. PLANNED ANALYSIS

For End-Of-Text tables, the set of summary statistics is: N / Mean / Standard Deviation (STD) / Min / Median / Max.

For tables that are provided for endpoints with some extreme data, median, quartiles and percentiles are preferred to mean, standard deviation, minimum and maximum.

In general, means, medians, and percentiles are presented to one more decimal place than the raw data and STDs are presented to two more decimal places than the raw data. Minima and Maxima are presented to the same number of decimal places as the raw data.

Tabulations of frequencies for categorical data include all possible categories (even if there is no count in a category) and display the number of observations in a category as well as the percentage (%) relative to the number of subjects in the respective treatment group (unless otherwise specified, all subjects in the respective subject set whether they have non-missing values or not). Percentages are rounded to one decimal place, unless the denominator is smaller than 100 (in all treatment columns), in which case percentages are rounded to the nearest integer. The category missing will be displayed only if there are actually missing values.

If a table presents only categorical data, “[N (%)]” is displayed in the column header only.

Abbreviations (e.g. Wors.) or acronyms (e.g. PD) will not be displayed in tables and subject data listings without any explanation. They will be either spelled out or explained in footnotes.

If applicable, days will be converted to weeks, months or years as follows:

- weeks = days \div 7
- months = $12 \times$ days \div 365.25
- years = days \div 365.25

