### 5.2.6.2 Adverse event collection and reporting

#### 5.2.6.2.1 AE Collection

The investigator shall maintain and keep detailed records of all AEs in the patient files.

The following must be collected and documented on the appropriate CRF(s) by the investigator:

- **For patients who roll-over to the extension trial:**
  - From signing informed consent onwards until first dose of trial medication in the extension trial: all AEs (serious and non-serious) and all AESIs. Updates to

concomitant therapy should also be included until first dose of trial medication in the extension trial.

**Note:** Updates for SAEs and/ or AESIs ongoing at the time of rollover to the extension trial, must be also updated in parent trial, in addition to the extension trial, as long as the data base of parent trial is not locked. On SAE form, updates for events reportable on SAE form with onset in parent trial are only reported into the parent trial.

- **For patients who do not roll-over to the extension trial:**
  - From signing the informed consent onwards until the 28 days (F2 visit) after the end of treatment visit: all AEs (serious and non-serious) and all AESIs.
  - **After the individual patient's end of trial:** The investigator does not need to actively monitor the patient for new AEs but should only report any occurrence of cancer and trial treatment related SAEs and trial treatment related AESIs of which the investigator may become aware of by any means of communication, e.g. phone call. Those AEs should be reported on the BI SAE form (see section 5.2.6.2.2), but not on the CRF.
- **For patients who permanently discontinue trial medication prematurely:**
  - From signing the informed consent onwards until the 28 days (Follow-up 2 visit) after the early end of treatment visit: all AEs (serious and non-serious) and all AESIs.
  - **From Follow-up 2 visit up to the individual patients' planned end of Trial (i.e. 26 weeks/visit 11):** Until the individual patient's planned end of trial, the investigator must report
    - Treatment related SAEs / AESIs
    - Following regardless of causal relationship
      - Anaemia
      - SAEs from C-SSRS assessments
      - Any occurrence of cancer
      - Deaths/ fatal AEs

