### 6.2.4 Follow up of Treatment completers

#### 6.2.4.1 Trial completers rolling-over to the extension trial

Patients who complete the 26 weeks treatment in 1346-0011 and are willing to participate in the open label extension trial with Iclepertin 10mg ([c33088336](#)):

- The patient completing the 26 week treatment period will be considered as treatment and trial completer. If the patient rolls over into the extension trial at the EOT visit (preferred option), the Follow up period visits (14 and 28 days follow up visit) **do not have to be completed**. Termination of trial medication and trial completion eCRF pages will be completed with same visit date.
- The patient will start participation in the open label extension trial with Iclepertin 10mg ([c33088336](#)).
  - This extension study is conducted under a separate trial protocol and patients will need to provide consent to participate in the extension trial.
  - These patients may enter the extension trial (Visit 1) either (preferably) on the day of EOT or at the latest 2 weeks after the EOT visit (i.e. Follow up 1 timepoint including the applicable time windows).
  - If patient decides to roll over between day 1- 7 after EOT, no safety laboratory assessment needs to be done unless medically required.
  - If patient decides to roll over between day 8 – 14 after EOT, the assessments according to Follow up visit 2 shall be completed instead of Follow-up visit 1.
  - If patients decide, at the latest 2 weeks after the EOT visit, not to roll-over to extension, please follow the instructions in [Section 6.2.4.2](#).

- Further details will be provided in the 1346-0014 protocol ([c33088336](#)).

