6. GENERAL ANALYSIS DEFINITIONS

6.1 TREATMENT(S)

For basic study information on treatments to be administered, assignment of treatment groups, select of doses, see CTP Section 4.

Table 6.1: 1 lists the two treatment groups in this study. Table 6.1: 2 defines the analysing treatment period for safety analyses. For this study, the residual effect period (REP) is defined as 12 days after the last dose of trial medication.

Table 6.1: 1 Treatment descriptions

Long Name	Short Name
Placebo	Placebo
Iclepertin 10 mg QD	Iclepertin 10 mg

Table 6.1: 2 Analysing treatment periods (same for all treatment groups)

Analysing Treatment Period	Start Date	End Date
Screening period	Date of informed consent	Date of the first treatment administration – 1 day
On-treatment period	Date of the first treatment administration	Date of the last treatment administration + REP
Post-treatment period	Date of the last treatment administration + REP + 1 day	Date of the last per protocol visit

REP is the residual effect period which is defined as 12 days after the last dose of trial treatment.

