7.8 SAFETY ANALYSIS

All safety analyses will be performed on the treated set and other subject sets as appropriate.

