7.8.1 Adverse events

Unless otherwise specified, the analyses of AEs will be descriptive in nature. All analyses of AEs will be based on the number of subjects with AEs and not on the number of AEs. The reporting and analyses of AEs will follow the BI guideline (3). AEs will be coded with the most current version of MedDRA®.

For further details on summarization of AE data, please refer to (1, 3).

The analysis of AEs will be based on the concept of treatment emergent AEs. That means that all AEs occurring between the date of the first administration of trial treatment till the date of the last administration of trial treatment + residual effect period will be assigned to the on-treatment period. All AEs occurring before the first administration of trial treatment will be assigned to 'screening' and all AEs occurring after the residual effect period will be assigned to 'follow-up'. For details on the treatment definition, see [Section 6.1](#).

Adverse events of special interest (AESIs)

A hepatic injury is defined by the following alterations of hepatic laboratory parameters:

- an elevation of AST and / or ALT ≥ 3 fold ULN combined with an elevation of total bilirubin ≥ 2 fold ULN measured in the same blood draw sample; and / or
- marked peak aminotransferase (ALT and / or AST) elevations ≥ 10 fold ULN.

See CTP Section 5.2.6.1.

Other significant AEs

User-defined AE category	MedDRA preferred terms	
Drug abuse, dependence, withdrawal and substance-related disorders, including diversion	Accidental death	Intentional overdose
	Drug abuse	Muscle rigidity
	Accidental overdose	Nasal necrosis
	Accidental poisoning	Nasal septum perforation
	Dependence	Nasal septum ulceration
	Drug abuser	Needle track marks
	Product administered at inappropriate site	Neonatal complications of substance abuse
	Drug dependence	Overdose
	Drug detoxification	Poisoning
	Drug dependence antepartum	Poisoning deliberate
	Drug dependence, postpartum	Substance dependence
	Drug diversion	Prescription form tampering
	Drug tolerance	Product tampering
	Drug tolerance increased	Product used for unknown indication
	Toxicity to various agents	Rebound effect
	Drug use disorder	Seizure
	Drug use disorder antepartum	Status epilepticus
	Drug use disorder, postpartum	Substance abuse
	Drug withdrawal convulsions	Substance abuser
	Drug withdrawal headache	Substance use
	Drug withdrawal syndrome	Substance use disorder
	Drug withdrawal syndrome neonatal	Substance-induced mood disorder

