An overall summary of adverse events will be presented, including frequency of schizophrenia relapse. The frequency of subjects with AEs will be summarised by treatment, primary system organ class (SOC) and preferred term (PT). The SOCs will be sorted by default in descending frequency and PTs will be sorted in descending frequency within an SOC in the iclepirtin arm. Separate tables will be provided for patients with

- Related AEs
- Serious AEs
- Serious related AEs
- AESIs
- Other significant AEs
- AEs leading to death
- AE leading to discontinuation of trial medication
- AEs occurred with incidence in the preferred term >2%
- AEs suggestive of abuse potential or related to CNS depressant effects
- AEs in user-defined AE categories
- AEs occurred during the follow-up period.

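### Under the SAP's default denominator, the follow-up adverse event table counts extension rollovers who have little or no follow-up observation, so its percentages understate the risk among patients actually observed

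*SAP*

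**What the plan says.** **The table.** SAP 7.8.1 lists separate tables by type of event, one of them for "AEs occurred during the follow-up period". The same section assigns an AE to follow-up if it occurs after the residual effect period (REP). SAP 6.1 sets the REP at 12 days after the last dose, and Table 6.1: 2 starts the post-treatment period on "Date of the last treatment administration + REP + 1 day" and ends it at the last per-protocol visit.

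**The denominator.** SAP 7.8 states: "All safety analyses will be performed on the treated set and other subject sets as appropriate". For frequency tables, SAP 7 makes the percentage relative to the number of subjects in the treatment group. Unless otherwise specified, that means "all subjects in the respective subject set whether they have non-missing values or not". SAP 7.8.1 gives no different base for the follow-up table, and SAP 6.4 defines no set of patients who entered follow-up.

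**What is collected.**
- For patients who roll over, protocol 5.2.6.2.1 sets the collection window as "From signing informed consent onwards until first dose of trial medication in the extension trial: all AEs (serious and non-serious) and all AESIs".
- Protocol 6.2.4.1 covers the visits: "If the patient rolls over into the extension trial at the EOT visit (preferred option), the Follow up period visits" need not be done. Rollover is allowed up to 2 weeks after EOT, including the Follow-up 1 window.
- Completers who do not roll over have full AE collection to Follow-up 2, 28 days after EOT.
- Early stoppers have full collection to 28 days after the early EOT visit. From then to week 26 only a restricted list is reported: treatment-related serious AEs and AEs of special interest, plus anaemia, serious AEs from the C-SSRS, cancer and deaths.

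**The concern.** A patient who takes the preferred route into the extension cannot contribute a follow-up AE to this trial's table, but under the default rule still adds one to its denominator. The table then prints events per treated patient, and a reader will tend to take that as the risk of an event after stopping.

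This matters because protocol 1.4.2 says that events after stopping have not been formally investigated and cannot be fully excluded, and protocol 5.2.6.6 asks for close monitoring of exactly the patients who do not roll over. They are the ones whose risk is diluted, and nothing in the planned table would show how many of them there were.

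There is a second, smaller problem. The post-treatment period of early stoppers runs on past Follow-up 2, so the table would pool a stretch of full AE collection with a stretch in which only selected events are reported.

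**Working it through.** The documents state no follow-up AE rate and no rollover share, so there is no plan figure to reproduce for this table. The arm size used for counts does reproduce: 220 / (1 - 0.25) = 293.3, against 293 per arm in protocol 7.5.

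**Step 1: time at risk.** The last dose is taken on the day before EOT (protocol 4.1.4), i.e. on EOT-1. SAP follow-up therefore starts on EOT - 1 + 12 + 1 = EOT+12. I assume that the first extension dose is taken on the day of rollover.

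| Patient | Days in SAP follow-up with AE collection |
|---|---|
| Rolls over from EOT to EOT+12 | 0 full days |
| Rolls over at EOT+14 | 14 - 12 = 2 |
| Rolls over at EOT+17 (end of the Follow-up 1 window) | 17 - 12 = 5 |
| Completer, no rollover, to EOT+28 | 28 - 12 + 1 = 17 |

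**Step 2: share of the Treated Set that is observable.** Let s be the early-stopping share, 0.30 to 0.40 (protocol 7.5, projected for the trial as a whole). Let r be the share of completers who roll over before any follow-up time accrues. It is not in the documents, so I assume 0.5 to 0.9. If every early stopper is followed:

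observable share = s + (1 - s)(1 - r)

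| r | s = 0.30 | s = 0.40 |
|---|---|---|
| 0.5 | 0.30 + 0.70 × 0.5 = 0.65 | 0.40 + 0.60 × 0.5 = 0.70 |
| 0.7 | 0.30 + 0.70 × 0.3 = 0.51 | 0.40 + 0.60 × 0.3 = 0.58 |
| 0.9 | 0.30 + 0.70 × 0.1 = 0.37 | 0.40 + 0.60 × 0.1 = 0.46 |

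With 293 per arm, the extremes are 0.37 × 293 = 108 and 0.70 × 293 = 205 observable patients.

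**Step 3: dilution.** Printed percentage = risk among observed patients × observable share. An illustrative 10% risk prints as 3.7% to 7.0%, an understatement of 30% to 63%. The relative understatement does not depend on the 10%. It reaches 10% once (1 - s) × r = 0.10, that is at r = 0.10/0.70 = 14% or r = 0.10/0.60 = 17%.

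**Step 4: arms.** If s and r are the same in both arms, both are diluted equally and no difference arises. Now suppose, purely for illustration, 40% versus 30% early stopping and equal true risk, and let f be the share of early stoppers actually followed. The observable share becomes s × f + (1 - s)(1 - r), and the arm ratio is:

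| f | r = 0.8 | r = 0.5 |
|---|---|---|
| 1 | 0.52/0.44 = 1.18 | 0.70/0.65 = 1.08 |
| 0.5 | 0.32/0.29 = 1.10 | 0.50/0.50 = 1.00 |
| 0.25 | 0.22/0.215 = 1.02 | 0.40/0.425 = 0.94 |

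The lower values of f borrow the 25-50% that protocol 7.5 expects for efficacy data after stopping. Safety capture may be higher, because protocol 6.2.5.1 offers a safety-only option. Partial follow-up shrinks or reverses the arm ratio but makes the dilution in step 3 worse.

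**The case against.** **The denominator is only a default.** SAP 7 says unless otherwise specified, SAP 7.8 allows other subject sets as appropriate, and SAP 7.8.1 defers AE summarisation to internal guides that are not among the documents. Under Table 6.1: 2, the post-treatment period of a patient who rolls over at EOT would start after the last per-protocol visit. It is therefore empty, and a programmer might leave such patients out. This stands as a limit: the documents do not show that the table will be wrong, only that the one visible rule makes it so and nothing visible overrides it.

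**Some rollovers are observed.** A reader might infer that no rollover patient has any follow-up. That goes too far. Late rollovers can have 2 to 5 days, and those on days 8-14 complete the Follow-up 2 assessments.

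**This is not the programme's main evidence on stopping.** A reader might infer that a withdrawal effect could go unseen. The first 12 days off drug count as on-treatment, so early events fall in the main tables. SAP Table 7.8.1: 1 has a category that includes withdrawal syndrome and rebound effect. Protocol 1.4.2 assigns close four-week monitoring of all completers to a parallel phase III trial (1346-0012). All of this stands and lowers the stakes, but it does not make this table's percentages right.

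**The arm difference is assumed.** The protocol gives neither stopping nor rollover by arm. Haemoglobin-driven withdrawal, and the exclusion of those patients from the extension (protocol 5.2.6.4), make a difference plausible but do not establish one. Even 5.2% versus 4.4%, about 15 versus 13 of 293 patients, is a 0.8-point gap against a standard error of about 1.8 points.

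**A restricted denominator is a post-randomisation subset.** Stoppers and non-rollover completers may differ in risk. This stands, and is a reason to keep arm comparisons descriptive.

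**Conclusion.** The concern holds as a dilution under the SAP's default rule. Patients who roll over by EOT+12 cannot have a recorded follow-up AE but are counted as event-free. The direction is certain whenever any patient does so. The size rests on the assumed 50-90% rollover, the protocol's 30-40% early stopping, and follow-up of every stopper: on that basis a 10% risk prints as 3.7-7.0%.

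The documents do not support reading this as a bias between arms of known size or direction. The illustrative ratio runs from 0.94 to 1.18 over the cases shown in step 4, and is 1.00 when stopping, rollover and follow-up are equal. Nor is any inference at risk, because the safety analyses are descriptive and carry no hypothesis test. The point is a misleading percentage in one safety table, worth correcting because the correction is cheap.

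**What to change.** In SAP 7.8.1, before treatment information is released:

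1. State that the follow-up AE table uses as denominator the Treated Set patients whose AE observation extends beyond last dose + REP, and print that N for each arm.
2. Limit the table to the period of full AE collection: from last dose + REP + 1 day to Follow-up 2 or the first extension dose, whichever is earlier.
3. List the restricted events reported for early stoppers after Follow-up 2 separately.

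Showing completers and early stoppers in separate columns, or adding rates per patient-week so that late rollovers count only for the days observed, would help but is optional.

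The cost is a few lines of SAP text and one changed table program plus a listing. The dates needed (last dose, Follow-up 2, first extension dose) already determine the collection windows, so no new data are required. The downsides are a smaller N, less favourable percentages, and a denominator formed after randomisation, so a sentence should say that arm comparisons in this table are descriptive only.

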7.1 DEMOGRAPHIC AND OTHER BASELINE CHARACTERISTICS

Only descriptive statistics are planned for this section of the report.

7.2 CONCOMITANT DISEASES AND MEDICATION

Only descriptive statistics are planned for this section of the report.

Concomitant diseases will be coded similarly as AEs based on the most current MedDRA version. A summary of concomitant diseases will be provided by treatment group, system organ class (SOC), and preferred term (PT).

Concomitant therapies (CTs) will be coded according to WHO DD and classified by the Anatomical, Therapeutic, Chemical (ATC) classification system. The third ATC level will be

used to categorise CTs by therapy type. In situations where a medical product may be used for more than one equally important indication, there are often several classification alternatives. As appropriate, subjects receiving CTs with more than one possible ATC level-three category will be counted more than once. CTs will be summarised in two groups: CNS-active and non-CNS-active concomitant medications.

Summaries will also be provided for the following CTs of special interest: antipsychotics, benzodiazepines, anticholinergics, antiepileptics, and antidepressants, as defined in [Table 10.7: 1](#).

7.3 TREATMENT COMPLIANCE

Only descriptive statistics are planned for this section of the report. See [Section 5.4](#) for definitions of treatment compliance. In addition, descriptive statistics of treatment adherence based on the AiCure data, as defined in [Section 5.4](#), will also be reported.

7.4 PRIMARY ENDPOINT ANALYSIS

7.4.1 Primary analysis

In the primary analysis under the primary estimand, intercurrent events will be addressed using a strategy that differs depending upon the nature of the intercurrent event. For details please refer to [Section 6.3](#) above (or Section 7 of the CTP). This primary analysis of the primary efficacy endpoint will be performed on the Randomized Set. With regard to the stratification factor, subjects will be analyzed according to the screening MCCB overall composite T-score stratum to which they correctly belong. Missing data resulting from the strategy (including both actual missing outcomes and excluded outcomes) will be handled using a mixed-effects model for repeated measures (MMRM) under the assumption of missing at random.

The primary endpoint is the change from baseline to Week 26 in overall composite T-score of the MCCB.

The primary analysis will be a restricted maximum likelihood (REML) based approach using a mixed-effects model for repeated measurements (MMRM) comparing the change from baseline in MCCB overall composite T-score at Week 26 between icleperitin 10 mg QD and placebo. The MMRM will include the fixed categorical effects of treatment at each visit, a fixed categorical effect of the stratification factor using the screening MCCB overall composite T-score, and a fixed effect for the continuous covariate of baseline (i.e. baseline MCCB overall composite T-score) at each visit. Visit will be treated as the repeated measure with an unstructured covariance structure used to model the within-subject dependencies.

The statistical model will be as follows:

$$y_{ijkm} = \beta_j S_i + \tau_{jk} + \varphi_m + e_{ij},$$

where

$$(e_{i1}, \dots, e_{iJ})' \sim N_J(\mathbf{0}, \Sigma),$$

and

y_{ijkm} = response variable for subject i in stratum m at visit j randomized to treatment k

S_i = the baseline MCCB overall composite T-score of subject i , $i = 1, 2, \dots$

β_j = coefficient of baseline effect at visit j , $j = 1, \dots, J$

τ_{jk} = the effect of treatment k at visit j , $k = 1, 2$

[figure not shown]
φ_m = the effect of screening MCCB overall composite T-score stratum m for $m = 1, 2$,
and $\varphi_1 \equiv 0$ for stratum 1 of T-score < 30

[figure not shown]
e_{ij} = the random error associated with j th visit of the i th subject.

[figure not shown]
Σ = a $J \times J$ unstructured covariance matrix

[figure not shown]
The Kenward-Roger approximation will be used to estimate the denominator degrees of freedom and adjust standard errors. Significance tests will be based on least-squares means, following the testing strategy described in CTP Section 7.1. The primary treatment comparison will be the contrast between icleperitin 10 mg QD and placebo at Week 26. Results of the MMRM (N, mean, SE and 95% CI per dose group and timepoint) will be presented in tables and displayed graphically.

Example SAS code for the primary analysis of MMRM is provided in [Section 10.2.1](#). In the event of non-convergence, methods described in [Section 10.2.2](#) will be attempted to overcome the issue.

[figure not shown]
